#### 14.7.2 Confidentiality and ownership of study data

Any confidential information relating to the IP or the study, including any data and results from the study, will be the exclusive property of the Sponsor. The Investigator and any other persons involved in the study will protect the confidentiality of this proprietary information belonging to the Sponsor.

#### 14.7.3 Publication

The results from this study will be submitted for publication at the discretion of the Sponsor.

### 14.8 Archiving

The Principal Investigator is responsible for maintaining essential documents, for 10 years after finalization of the Clinical Study Report. This includes any original source documents related to the study, the Subject Identification List (providing the sole link between named subject source records and anonymous CRF data), the original signed ICFs and detailed records of disposition of IP.

It is the responsibility of the Sponsor to inform the Principal Investigator/institution as to when these documents no longer need to be retained.

The Sponsor will archive the Trial Master File (TMF) and applicable regulatory requirements.

## 15 DATA MANAGEMENT

### 15.1 Case Report Forms

#### 15.1.1 Viedoc™

Data will be collected in eCRFs (Viedoc™) specifically designed for this study. The Investigator or an authorized person will record subject data in the eCRF in a precise and accurate manner. Abbreviations should not be used. The Investigator is responsible for the data entered and sign off the eCRF at each visit and at the end of the study. The data should be recorded as soon as they are generated. Only persons authorized by the Investigator are allowed to make entries to the eCRF.

An electronic diary will be used by the subject during the study period for recording of occurrence of UTI symptoms and sexual activity.

#### 15.1.2 ViedocMe™

An electronic diary will be used by the subject during the study period for recording of occurrence of UTI symptoms and sexual activity (frequency of intercourse, new partner, use of condom with spermicide). A separate invitation will be sent to each included subject directly from the Viedoc™ system. The CTC AB clinic will save the sent-out invitation for security purpose. The invitation will consist of a URL, Username and Passcode. The subject will be by the system advised to change the pass code at first login.

## 15.2 Data management plan and database design

Detailed information on data management will be described in a study-specific Data Management Plan (DMP).

The person entering data into the database is not allowed to attempt any personal interpretation or to make any decisions on the data other than self-evident corrections as listed in the study-specific Data Entry Instructions or Data Handling Report.

Data validation/data cleaning procedures are designed to assure validity and accuracy of clinical data. These procedures consist of manual reviewing during data entry and computerized edit checks and queries for identifying data values that are outside the allowed range, protocol violations, incomplete or inconsistent. A Data Validation Plan (DVP) will specify the checks that are to be performed on subject data for the study. All study-specific and standard data validation programming will be tested in a separate testing environment prior to use on production data.

Queries in Viedoc™ can be raised by Monitors, Data Managers, medical coding team, and medical safety representatives. Queries raised may be related to missing or questionable data found during data validation, SDV, review, reconciliation of SAEs, and/or coding of study data. All queries should be written and answered in English.

The Investigator or designated site personnel will provide answers to all queries by giving a clear explanation to the question asked. The site Monitor is responsible for approving the resolved query. In case the answer to a query was not satisfactory the query should be rejected and re-phrased if needed. Rejected queries will be re-issued automatically and listed as unresolved.

### 15.2.1 Database lock

When all data have been entered, discrepancies solved and all reconciliation with the SAE database is complete, the database will be locked and the data will be analysed.

## 16 STATISTICAL METHODS AND DETERMINATION OF SAMPLE SIZE

The principal features of the statistical analysis to be performed are described in this section. A more technical and detailed elaboration of the principal features will be presented in a separate Statistical Analysis Plan (SAP).

### 16.1 General

Data on continuous variables will be presented using summary statistics. Data will be presented in terms of number (N), arithmetic mean, standard deviation (SD), minimum and maximum value.

Categorical data will be presented as counts and percentages. Individual subject data will be listed by randomization number, and where applicable by assessment time.

All statistical tests will be performed using a two-sided hypothesis with a significance level of 5%.

## **16.2 Determination of sample size**

Hypothesis:

$H_0$ : Mean number of UTIs in Probiotic group = Mean number of UTIs in the placebo group

$H_1$ : Mean number of UTIs in Probiotic group  $\neq$  Mean number of UTIs in the placebo group

The number of subjects needed to verify that the mean number of UTIs during six months for the probiotic will be 0.75 and for placebo 1.35 with a common standard deviation of 1.15, will be 118 (1:1 randomization) using a significance level of 5% and a power of 80%.

Assuming a drop-out rate of 15% a total of 140 subjects will be included.

## **16.3 Analysis data sets**

### **16.3.1 Full Analysis Set**

The Full Analysis Set (FAS) will consist of all subjects who have been randomized and received at least one dose of intervention.

### **16.3.2 Per Protocol Set**

The Per Protocol Set (PPS) will consist of all subjects who have been randomized, completed the three months of intervention period and without any major protocol deviations. All deviations will be presented and discussed at the clean file meeting. If the compliance with the IP regimen should be below 80% the subject will not be included in the PPS population. The definition of compliance is by calculating the number of delivered products in relation to the number of unused IP as reported by the subject.

## **16.4 Description of study population**

### **16.4.1 Demographics and baseline data**

Summary statistics of demographics and other baseline characteristics will be presented by intervention group.

### **16.4.2 Medical history and concomitant medications**

Medical/surgical history and prior/concomitant medications/products will be presented by descriptive statistics and listings by intervention.

### **16.4.3 UTI history**

The number of previous UTIs (prior to screening) will be presented using frequency tables.

### **16.4.4 Compliance with the intervention**

Compliance with the intervention will be calculated as number of delivered products divided by number of reported unused products and presented using summary statistics.

## 16.5 Analysis of primary endpoint

The primary endpoint will be the mean number of confirmed UTIs during six months from start of intervention, as compared to placebo.

The mean number of UTIs per intervention group will be estimated based on the total number of UTIs by subject.

The mean number of UTIs will be analysed using analysis of covariance with intervention, UTI history, age, and sexual activity as independent variables. No intervention by centre interaction will be possible to apply in this analysis. The estimated intervention difference will be presented by LSMeans and a 95% confidence interval.

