### **Duration of intervention**

The IP will be taken for three months (90 days).

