5 SUBJECTS

5.1 Subject Disposition

The number of subjects that entered the study, withdrawn subjects, completed subjects and the number of subjects at each visit will be summarized by treatment.

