7.1 Primary endpoint(s) Analysis

The primary endpoint will be the mean number of confirmed UTIs during six months from start of intervention, as compared to placebo.

The mean number of UTIs per intervention group will be estimated based on the total number of UTIs by subject.

An additional analysis will be made to include the subjects who have been used prohibited medications, long term antibiotics and Hiprex during the study.

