7.1.3 Supplementary analyses

No supplementary analysis for primary endpoint(s) will be performed.

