7.2 Secondary Endpoint(s) Analysis

7.2.1 Definition of endpoint(s)

7.2.1.1 Number of confirmed UTIs

The number of confirmed UTIs for both the:

- Mean number of confirmed UTIs during the three months' intervention period, as compared to placebo.

and

- Mean number of confirmed UTIs during the three months' follow-up period, as compared to placebo.

will be analysed using the same methods as for the primary endpoint.

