7.4 Discontinuation

Patients who discontinue from IMP treatment will be tabulated. The reason for discontinuation will be given. For discontinuation due to AE, the AEs will be given.

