13.3 Subject disposition and exposure

TABLE 14.1.1.2 SUBJECT DISPOSITION

	Treatment A	Treatment B	Total
Screened subjects	xx	xx	xx
Subjects that entered the study	xx	xx	xx
Withdrawn subjects	xx	xx	xx
Completed subjects	xx	xx	xx
Included in FAS	xx	xx	xx
Included in PPS*	xx	xx	xx
Subjects at Screening	xx	xx	xx
Subjects at Visit 2	xx	xx	xx
Subjects at Visit 3	xx	xx	xx
Subjects at Visit 4	xx	xx	xx
Subjects at Visit 5	xx	xx	xx

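### Early leavers' partial UTI counts enter the primary ANCOVA as six-month totals with no follow-up adjustment or sensitivity analysis; the SAP contradicts itself on imputation and extra analyses, and 140 is misstated as completers

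*Protocol*

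**What the plan says.** **Primary analysis.** Protocol 16.5 says: "The mean number of UTIs per intervention group will be estimated based on the total number of UTIs by subject". SAP 7.1 repeats this. The model (SAP 7.1.1) is an ANCOVA with intervention, UTI history and age, plus sexual activity if possible. It has no offset or follow-up-time term. The Full Analysis Set (Protocol 16.3.1) takes in every randomised woman with at least one dose. Protocol 10.7.1 uses all data collected up to discontinuation. Protocol 16.8.2 and SAP 4.7 exclude imputation, and SAP 7.1.2 excludes a sensitivity analysis.

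**Secondary endpoints.** The UTI counts for the intervention period and the follow-up period "will be analysed using the same methods as for the primary endpoint" (SAP 7.2.1.1). The relapse proportions use a chi-square test, and nothing is said about leavers (SAP 7.2.1.3). Only the Cox analysis handles incomplete follow-up, by censoring at the last known date (SAP 7.2.1.2).

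**Imputation.** The estimand table in SAP 3.1 gives multiple imputation for the primary ANCOVA and reference-based multiple imputation as a sensitivity analysis.

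**Extra analyses.** SAP 7.1 says: "An additional analysis will be made to include the subjects who have been used prohibited medications, long term antibiotics and Hiprex during the study". SAP 7.1.3 says: "No supplementary analysis for primary endpoint(s) will be performed".

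**Sample size.** The synopsis (number of subjects planned), Protocol 10.3 and SAP 4.1 require 140 completed subjects. The synopsis (statistical methods), Protocol 16.2 and SAP 3.4 have 140 included after allowing for 15% drop-out. Protocol section 4 defines an included subject as one randomised and a completed subject as one who finished both periods. Protocol 10.7.2 rules out replacement.

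**The concern.** A raw total treats a woman seen for one month and a woman seen for six as equally observed. Every month lost counts as a month without UTI. If the two arms lose similar amounts of follow-up, both means shrink and the difference is diluted. If one arm loses more, that arm looks better for a reason unrelated to the product.

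The problem is sharpest for the follow-up-period endpoint. A woman who leaves before Day 90 is in the Full Analysis Set with no observed time in months 4–6, and the same method would score her zero. The chi-square test would likewise count a leaver without a UTI as relapse-free.

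No planned analysis of the primary endpoint shows whether the result survives unequal follow-up. The contradictions on imputation and additional analyses leave room to dispute, after unblinding, which primary analysis was intended. The two meanings of 140 give two recruitment targets.

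**Working it through.** **1. Reproduce the sample size.** Inputs from Protocol 16.2: means 0.75 and 1.35 (difference 0.60), SD 1.15, two-sided 5%, power 80%, drop-out 15%.
- Normal approximation: 2 × (1.96 + 0.8416)² × 1.15² / 0.60² = 57.7, so 58 per arm.
- Two-sample t-test: 58.64, so 59 per arm, 118 in total, power 80.2%. This matches the plan.
- 118 / 0.85 = 138.8, which becomes 140 with equal arms. So 140 is the number randomised.
- 140 × 0.85 = 119 completers, power 80.6%.
- 140 completers would need 140 / 0.85 = 164.7, so 165 randomised. With 70 completers per arm, power would be 86.5%, not the 80% planned for.

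**2. Expected effect of partial totals.** Assume exits spread uniformly over six months. A leaver is then seen for half the period on average, and an arm with drop-out d has its mean multiplied by (1 − 0.5d). Differences are active minus placebo.
- True effect, 15% in both arms: −0.60 × 0.925 = −0.555.
- True effect, placebo 20%, active 10%: 0.75 × 0.95 − 1.35 × 0.90 = 0.7125 − 1.215 = −0.5025.
- True effect, placebo 10%, active 20%: 0.75 × 0.90 − 1.35 × 0.95 = 0.675 − 1.2825 = −0.6075.
- No effect (mean 1.35 in both arms), placebo 10%, active 20%: −1.35 × 0.5 × 0.10 = −0.0675.
- No effect, placebo 5%, active 25%: −1.35 × 0.5 × 0.20 = −0.135.

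**3. Power and type I error, by simulation.** 70 per arm, gamma-Poisson counts, t-test on raw totals. Two variance models were used:
- Overdispersion 0.2285, which makes the average variance 1.15²: (1.35 + 0.2285 × 1.35² + 0.75 + 0.2285 × 0.75²) / 2 = 1.3225. The arm SDs are about 1.33 and 0.94.
- SD near 1.15 in each arm.

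| Drop-out, placebo/active | True difference | Estimate | Result |
|---|---|---|---|
| 15/15 | −0.60 | about −0.555 | power 81–84% |
| 20/10 | −0.60 | about −0.50 | power 73–77% |
| 15/15 | 0 | about 0 | type I error about 5% |
| 10/20 | 0 | about −0.07 | type I error 6.2–6.5% |
| 5/25 (extreme) | 0 | about −0.13 | type I error 9–11% |

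An ANCOVA adjusted for an assumed UTI history and age, under the first variance model, agrees: −0.554 and 85% power at 15/15; −0.066 and 6.2% with no effect at 10/20.

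**4. An exposure-adjusted analysis on the same data.** UTIs per time at risk, estimated in months 0–3 and 3–6 and summed, give −0.60 at 15/15, 20/10 and 10/20, with type I error of 5.0–5.2% (first variance model). If a UTI itself prompts leaving (17% of UTIs, assumed), raw totals give −0.49 and the rate analysis −0.58. If 60%, 70% or 90% of active-arm UTIs fall in months 4–6, a single constant rate gives −0.605, −0.612 or −0.626; fitting by period gives −0.599, −0.600 or −0.602.

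**5. Secondary endpoints at 15/15, uniform exits.**
- Half the leavers go before month 3: 0.15 / 2 = 7.5% of women have no observed time in months 4–6. The other half lose on average half of that period, so the mean is multiplied by 1 − 0.75 × 0.15 = 0.8875. If half of the effect (−0.30) belongs to that period, the estimate is −0.30 × 0.8875 = −0.266.
- Six-month relapse, with leavers without a UTI counted as relapse-free (first variance model): 46.7% against 65.2%, instead of 50.0% against 69.2%. The gap is 18.5 points instead of 19.2.

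**6. Text set side by side.** SAP 3.1 (multiple imputation, and a sensitivity analysis) cannot be followed together with SAP 4.7 and 7.1.2. SAP 7.1 (an additional primary-endpoint analysis) cannot be followed together with SAP 7.1.3. The purpose of that addition is also unclear. The Full Analysis Set already includes users of prohibited medication. Only the Per Protocol Set excludes them (SAP 4.2.2), and SAP 4.2.3 limits that set to secondary objectives.

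**The case against.** The strongest reply is that the plan already has a rule in substance and that little follows from it. Most of this stands, and it limits the point in several ways.

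- A reader might infer that leavers' counts are wholly unregulated. Protocol 10.7.1, 16.3.1, 16.5 and 16.8.2 together imply that observed totals stand. The weakness is what that rule does to unobserved time, and that nothing checks it.
- A reader might infer that the type I error is inflated under the plan's own assumptions. It is not. The only documented drop-out is 15% overall, and with equal arms the error stays at about 5%. The larger figures need an assumed imbalance.
- A reader might expect a rate analysis to gain power. At equal drop-out, raw totals give 81–84% and rate models 79–85%, depending on the model. No gain should be claimed.
- A reader might infer that an imbalance would go unseen, because the disposition shell in SAP 13.3 ends at "Subjects at Visit 5". SAP 5.1 already requires that "the number of subjects at each visit will be summarized by treatment", so attendance will be visible. SAP 7.4 adds that "Patients who discontinue from IMP treatment will be tabulated" with reasons, though it does not say by arm. Seeing an imbalance is still not the same as having a planned analysis that allows for it.
- A reader might take SAP 7.1 to imply a hidden primary analysis that excludes users of prohibited medication. The sentence may only be clarifying that the Full Analysis Set includes them.
- The imputation rows look like unedited template text, since a cross-reference placeholder remains in the same table's footnotes. They nevertheless stand in the body of the SAP, and SAP section 8 does not mention them.
- The sample-size calculation is right. Only the word completed is wrong.

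**Conclusion.** The point holds as a robustness gap plus three textual contradictions. It is not a flaw that invalidates the design.

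At 15% drop-out in both arms the cost is dilution of about 0.045 UTIs (0.60 − 0.555), with power still above 80%. With unequal drop-out the primary estimate is biased in either direction: about 0.07 UTIs in favour of the active arm with no true effect at placebo 10%, active 20%, and about 0.10 lost from a true effect of 0.60 at placebo 20%, active 10%. The split by arm, the exit times and the variance model are assumptions; only the overall 15% comes from the documents.

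The plan's own arithmetic shows that 140 is the number to randomise. Calling it the number completed, in three places, is an error.

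**What to change.** - **Number of subjects.** In the synopsis, Protocol 10.3 and SAP 4.1, state 140 randomised, to give about 119 completers (118 needed). The protocol wording needs a numbered amendment under Protocol 13.5.
- **Sensitivity analysis (SAP 7.1.2).** Pre-specify one exposure-adjusted analysis of unique confirmed UTIs: robust Poisson or negative binomial, log time at risk as offset, the ANCOVA covariates and robust standard errors. Report the difference in mean UTIs per six months with 95% CI, and the rate ratio. The ANCOVA stays primary. Use the start of intervention and last known date of SAP 7.2.1.2, so that the Cox and rate analyses share one clock. Fitting by period (months 0–3 and 3–6) is preferable because product is taken for only three of the six months. It must then say how site-registered UTIs, which SAP 4.12 dates by telephone contact, are placed around month 3.
- **Three-month endpoints.** Exclude women with no observed time in months 4–6 from the follow-up-period ANCOVA. Also analyse both endpoints as rates, using each period's own time at risk.
- **Relapse proportions.** State how the chi-square test counts leavers without a UTI. Beside it, give Kaplan-Meier proportions at Days 90 and 180 with the difference and 95% CI.
- **Contradictions.** Reconcile SAP 3.1 with 4.7 and 7.1.2, and SAP 7.1 with 4.2.3 and 7.1.3.

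None of this needs extra patients or data, because the last known date is already required for the Cox analysis. Apart from the protocol wording on 140, these are SAP edits to make before unblinding. The price is a little more analysis and the assumption that leavers' UTI rates resemble those of women still observed.

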### **Statistical methods**

Hypothesis:

$H_0$ : Mean number of UTIs in Probiotic group = Mean number of UTIs in the placebo group

$H_1$ : Mean number of UTIs in Probiotic group  $\neq$  Mean number of UTIs in the placebo group

The number of subjects needed to verify that the mean number of UTIs during six months for the probiotic will be 0.75 and for placebo 1.35 with a common standard deviation of 1.15, will be 118 (1:1 randomization) using a significance level of 5% and a power of 80%. Assuming a drop-out rate of 15% a total of 140 subjects will be included.

Data on continuous variables will be presented using summary statistics. Data will be presented in terms of number (N), arithmetic mean, standard deviation (SD), minimum and maximum value.

Categorical data will be presented as counts and percentages. Individual subject data will be listed by randomization number, and where applicable by assessment time.

All statistical tests will be performed using a two-sided hypothesis with a significance level of 5%.

For the primary efficacy endpoint, the mean number of UTIs will be analysed using analysis of covariance with intervention, UTI history, age and sexual activity as independent variables. No intervention by centre interaction will be possible to apply in this analysis. The estimated intervention difference will be presented by LSMeans and a 95% confidence interval.

The Full Analysis Set (FAS) will consist of all subjects who have been randomized and received at least one dose of Intervention.

The Per Protocol Set (PPS) will consist of all subjects who have been randomized, completed the three months of intervention period and without any major protocol deviations. All deviations will be presented and discussed at the clean file meeting. If the compliance with the IP regimen should be below 80% the subject will not be included in the PPS population. The definition of compliance is by calculating the number of delivered products in relation to number of unused IP as reported by the subject.

A detailed Statistical Analysis Plan (SAP) will be approved and signed prior to clean file.

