## 9 INVESTIGATIONAL PLAN

### 9.1 Overall study design and schedule of events

This will be a double-blinded, randomized, placebo-controlled, parallel-group study with the primary objective to evaluate the effect of oral supplementation with *Lactobacillus reuteri* on the frequency of confirmed UTI in adult women with recurrent UTIs.

The study will consist of a combined screening and randomization assessment, an IP first dose confirmation call, and monthly follow up assessments for six months. The screening and randomization assessment will be performed as a phone call or a video-call using an e-health digital platform. Informed consent will be signed via Bank ID. The monthly follow-up assessments will be performed either as a video-call or by phone. However, physical visits to the clinic at CTC AB might be performed for subjects in Uppsala.

Female subjects 18-50 years of age with recurrent UTI and currently on antibiotic treatment for UTI will be recruited from advertising (e.g. in social media, at pharmacies, etc.).

Recurrent UTI is defined as occurrence of at least two UTIs during the last six months or at least three UTIs during the last 12 months, with a minimum period of two weeks between episodes, unless there is a urinary culture confirming two different pathogens. The subject will contact the study site by phone or e-mail. Brief oral information about the study will be given and pre-defined pre-screening questions will be asked. Written information will be sent to the subject qualified for screening together with instructions regarding the e-health platform and Bank ID signing procedures.

During the screening and randomization assessment, full information about the study will be given and informed consent obtained as described in Section 13.3. Information regarding demographics, weight, height, medical history, UTI history, medication history, use of restricted products, and pregnancy will be collected and diet restrictions will be explained (see Section 10.6). Subjects will be screened for eligibility as per the pre-defined eligibility criteria (see Sections 10.4 and 10.5).

Eligible and consenting subjects will be randomized to intervention with either *Lactobacillus reuteri* or placebo. The subjects will be provided with IP for three months (90 days) and niture/Leu urine test kits. Instructions to start intake of IP as soon as the IP has been picked-up will be given.

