## 10.5 Exclusion criteria

Subjects must not enter the study if any of the following exclusion criteria are fulfilled:

1. Postmenopausal (defined as 12 months of amenorrhoea).
2. Pregnant or breastfeeding.
3. Planning to become pregnant during the study.
4. Irregular menstruations combined with perimenopausal symptoms.
5. Known hypersensitivity or allergy to any of the components of the test product, or to the comparator (placebo).
6. Currently on long-term antibiotic treatment.
7. Use of spermicide contraceptives including spermicidal condom within three days prior to first IP dose.
8. History of complicated cystitis, urgency incontinence, recent pyelonephritis, urological and/or gynaecologist abnormalities, as judged by the Investigator.
9. Unstable bowel disorder such as chronic or recurring diarrhoea, Crohn's disease, ulcerative colitis.
10. History of any clinically significant disease or disorder which, in the opinion of the Investigator, may either put the subject at risk because of participation in the study, or influence the results or the subject's ability to participate in the study.
11. Participation in any other clinical interventional study within 30 days before treatment.

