### 10.6.2 Prior and concomitant therapy

No probiotic food supplements, probiotic foods or fermented food other than the test product, including vaginal products containing *Lactobacillus* (including probiotic tampons) or affecting the pH, are allowed from screening and throughout the study period.

Neither is any food or food supplements containing cranberries allowed from screening and throughout the study period. Subjects should continue with the same general diet and lifestyle, except probiotic and cranberry consumption.

Use of spermicide contraceptives including spermicidal condom will not be allowed during the study, up to Day 180.

Use of oral or vaginal fungicides will not be allowed during the study, up to Day 180. If typical vaginal candida symptoms appear (itching and typical thick, clumpy, white vaginal discharge) sporadic usage of oral fluconazole 150 mg as a single dose may be allowed and should be noted.

Subjects must not participate in any other clinical interventional study during the study period.

Other medications considered necessary for the subject's safety and well-being, may be used during the study period. In case of antibiotic use, the type and duration should be recorded. Any use of fluconazole, prohibited medication, therapies or products will require evaluation by the Investigator to determine whether or not the subject should continue in the study. This may be done in consultation with the Sponsor.

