### **12.3.2 Demographic information**

The following demographic data will be recorded: age, and ethnic origin.

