### **12.3.5 Urinary tract infection history**

Information regarding previous UTIs (diagnosis, prescriptions, etc.) during the last 12 months will be collected to confirm eligibility.

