## **16.8 Statistical/analytical issues**

### **16.8.1 Adjustments for covariates**

History of UTIs, age, and sexual activity will be used as covariates in the analysis of mean number of UTIs.

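### The primary ANCOVA includes sexual activity, which is recorded only after randomisation, and the SAP makes the term optional without a rule, a variable definition or a decision time

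*Protocol*

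**What the plan says.** **Model in the protocol.** Section 16.5 states "The mean number of UTIs will be analysed using analysis of covariance with intervention, UTI history, age, and sexual activity as independent variables". The synopsis repeats it ("analysis of covariance with intervention, UTI history, age and sexual activity as independent variables"), and so does 16.8.1 ("History of UTIs, age, and sexual activity will be used as covariates in the analysis of mean number of UTIs"). No condition is attached. Section 16.6.1 applies the same method to the two three-month counts.

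**Model in the SAP.** Sections 4.8, 7.1.1 and 7.2.3 name intervention, UTI history and age, and allow sexual activity only where its use is feasible. Section 8 lists this as a change from the protocol.

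**Where the data come from.** Screening, per protocol 9.1: "Information regarding demographics, weight, height, medical history, UTI history, medication history, use of restricted products, and pregnancy will be collected". Section 12.3.2: "The following demographic data will be recorded: age, and ethnic origin". Section 12.3.5: "Information regarding previous UTIs (diagnosis, prescriptions, etc.) during the last 12 months will be collected to confirm eligibility". None of these is an activity item. The nearest pre-dose item is exclusion criterion 7, "Use of spermicide contraceptives including spermicidal condom within three days prior to first IP dose", which concerns spermicide and does not measure activity. Sexual activity appears only in the electronic diary (12.2.2, 15.1.2), as three items: how often intercourse takes place, whether there is a new partner, and whether a spermicidal condom was used. Diary invitations go to included subjects (15.1.2), whom section 4 defines as randomised. Table 9.1 does not mark the diary at screening.

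**Surrounding rules.** SAP 4.7 plans no imputation. SAP 4.11 lists blind review as not applicable. SAP 7.1.2 and 7.1.3 plan no sensitivity or supplementary analysis of the primary endpoint.

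**The concern.** There are two separate problems.

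1. **The primary model is not fixed.** Two analysts could follow the SAP, one keeping the term and one dropping it, and report different primary results. They could also choose different diary items, periods or codings. The plan does not require the choice to be made before results are seen.

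2. **The optional term is a post-randomisation variable.** Adjusting for a pre-randomisation predictor leaves the target difference alone and sharpens it. Adjusting for something the outcome can alter does not. If a woman with a UTI abstains for a time, low recorded activity is partly a consequence of the UTI. Holding activity constant then removes part of any real treatment effect.

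The main risk is a missed effect. Type I error is a secondary risk: it rises if the more favourable model is the one reported, or if the product itself changes activity.

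**Working it through.** **The plan's own figure.** With means 0.75 and 1.35 (difference 0.60), SD 1.15, two-sided 5% and 80% power (protocol 16.2), a two-sample t-test needs 59 per arm, or 118 in total (power 80.2%). Then 118 / 0.85 = 138.8, consistent with 140. The calculation uses no covariate.

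**Assumed inputs.** The documents give no behavioural figures, so what follows is illustration, not bounds.
- Activity: mean 8 acts per month, SD 3 between women.
- Abstinence per UTI: 7, 21 or 35 days.
- Log UTI rate per SD of activity: 0, 0.2 or 0.3.
- Counts: over-dispersed, variance mean + 0.2285 × mean². This gives 1.766 at mean 1.35 and 0.879 at mean 0.75, averaging 1.3225 = 1.15².
- Two loss models: a fixed number of acts lost per UTI, or a loss proportional to the woman's own activity.

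**Closed form for the fixed loss (log rate 0).** Average monthly activity over six months is S = 8 + 3z - c × UTIs, with c = 8 × (days/30) / 6. With V = 1.3225, the adjusted difference is -0.60 × 9 / (9 + c²V).
- 7 days: c = 0.311, c²V = 0.128, giving -0.592.
- 21 days: c = 0.933, c²V = 1.152, giving -0.532.
- 35 days: c = 1.556, c²V = 3.200, giving -0.443.

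Simulation with 1,000,000 women per arm gives -0.594, -0.531 and -0.443.

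**Full ranges.** These cover both loss models and all three log rates. Power and error rates come from 100,000 trials of 59 per arm, fitted with and without S; UTI history and age are left out.

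| Abstinence per UTI | 1 week | 3 weeks | 5 weeks |
|---|---|---|---|
| Adjusted difference (true -0.60) | -0.59 to -0.61 | -0.52 to -0.58 | -0.40 to -0.49 |
| Power, adjusted (unadjusted 81-82%) | 80-83% | 74-78% | 55-67% |
| Models disagree on significance | 2-4% | 4-11% | 15-28% |
| Three-month difference (true -0.30, assumed) | -0.29 to -0.30 | -0.23 to -0.26 | -0.16 to -0.19 |

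**Type I error (mean 1.05 in both arms).** The adjusted test alone gives 4.9-5.2%. Always reporting the more favourable model gives 5.3-7.6%. If the product itself shifted recorded activity by 0.5 or 1 act per month, the adjusted test would give 4.9-7.8% or 5.1-17.5%; the documents give no reason to expect such a shift.

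**Missing diaries.** Without imputation, a woman with no usable covariate drops out of the adjusted model. Starting from 70 × 0.85 = 59.5 per arm, losing a further 10 / 20 / 30% lowers power from 81% to 76 / 71 / 65% (noncentral t).

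**The case against.** **Deleting the term also costs something.** If activity predicts UTIs and UTIs leave activity alone, adjustment gains power. At log rates of 0.2-0.3 per SD, the adjusted test has 82.3-84.1% power against 81.3-81.5% unadjusted, so about 1 to 3 points are given up. That range is not a ceiling, because the harm scenarios use stronger correlations (about -0.51 to -0.57). A correlation of 0.5 would put the cost near 9 points. The plan's own SD limits this, however. If activity explained all the over-dispersion, the log rate would be √ln(1.2285) = 0.454 and the within-arm correlation about 0.454 × 1.05 / 1.15 = 0.41. Power would then be 87.0% against 80.2%, a cost of about 7 points. The cost is real but limited.

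**Material harm needs strong assumptions.** This stands: at one week of abstinence nothing of note happens, and the 55-67% power needs five weeks per UTI.

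**The missing-diary figures stack losses.** This is partly fair. They assume that unusable diaries come on top of the 15% dropout. If 30% of 70 per arm were unusable in total, 49 per arm would remain, with about 72% power instead of 65%.

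**The SAP has already moved most of the way.** This is true: its unconditional terms are the right ones and the change is declared. What remains is an undefined optional clause, and that clause is the defect.

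**A pre-dose diary entry is conceivable.** Randomisation falls on Day -10 to 0 and first dose on Day 1, so an early window could satisfy the baseline definition in SAP 4.3. But Table 9.1 schedules no such entry and neither document defines such a window.

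**SAP 3.1 shows other primary and sensitivity analyses using multiple imputation.** That table contradicts SAP 4.7 and 7.1.2 and needs its own correction. It does not mention sexual activity, so it does not settle this point.

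**Recording spermicidal condoms is normal compliance monitoring.** This is accepted. Since 10.6.2 says "Use of spermicide contraceptives including spermicidal condom will not be allowed during the study, up to Day 180", the item is reasonable to record. The issue is only that nothing says whether it forms part of the covariate.

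**Conclusion.** The concern holds and should be fixed. Three facts need no behavioural assumption: the protocol and SAP differ on the primary model, the SAP's condition has no criterion or decision time, and the covariate is undefined and scheduled only after randomisation.

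The size of the bias does rest on assumptions. It ranges from nothing of note (one week of abstinence per UTI) to loss of about a fifth to a third of the true difference (five weeks: 0.11 / 0.60 = 18% to 0.20 / 0.60 = 33%). The direction is mainly towards no effect. The adjusted test alone keeps its 5% level unless the product changes activity, so inflation is chiefly a matter of choosing between models.

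SAP version 1 is dated August 2019, after the planned completion in Q4 2018. The documents do not say whether the choice of model was made blind, and nothing is inferred from that.

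**What to change.** Before unblinding:

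1. Fix the ANCOVA for the primary and both three-month counts as intervention + UTI history + age.
2. Remove sexual activity from SAP 4.8, 7.1.1 and 7.2.3, and replace the first item in SAP section 8 with this change and its reason.
3. Align the protocol synopsis, 16.5 and 16.8.1 by amendment under 13.5.
4. Report sexual activity by arm descriptively. Alternatively, fit one labelled exploratory model that names the diary item, period and coding, and list it in SAP 7.3, which at present plans no exploratory analysis.

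**Cost.** One SAP revision and one protocol amendment. The 118 evaluable / 140 randomised stand, because they rest on the unadjusted SD of 1.15. The power given up is about 1 to 3 points at the assumed log rates and about 7 at the limit set by the plan's SD, and only if activity predicts UTIs without being affected by them.
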